### **5. Data Safety and Monitoring Plan**

**Safety Monitoring:** Given the content of the questions and data collection methodologies, we anticipate minimal risk to participants. Answering questions about personal feelings and participating in the social stressor situation as part of the Trier Social Stress Task may have risk of causing emotional distress, particularly for participants who are experiencing high levels of social anxiety. The TSST-C has been well-validated for use in youth populations and has been widely used without causing undue risk to participants. For participants who are randomized to the conditions that involve interacting with a dog, there is always minor risk associated with interacting with live animals.

Although risks are minimal, we will provide participants with the PI's contact information should any questions or concerns arise, as well as provide contact information for mental health resources. We will also highlight the participant's right to discontinue his or her participation in any part of the study (including the TSST-C) at any time. If a participant becomes distressed during the TSST-C, the study will be stopped immediately, and the participant and his or her parent/guardian will be provided with contact information for a mental health professional. If any minor skin irritation or discomfort takes place as a result of wearing the E4 wristband, it will be removed immediately.

The animals participating in this study will be therapy dogs who are registered through Pet Partners® and members of Tufts Paws for People, reducing the risk of adverse events. The animals will always be accompanied by their handlers, who are required by Pet Partners to have their dogs on leash at all times while visiting and have been trained to advocate for their animals to ensure safety of all participants. The animal handlers are trained to recognize stress signals in their dogs and will discontinue participation immediately if the therapy animal becomes stressed.

**Reporting Adverse Events:** Though adverse events are not anticipated, if a participant becomes distressed during the study will be stopped immediately, and the participant and his or her parent/guardian will be provided with contact information for a mental health professional. If any animal handler or study personnel notice stress signals in the animal subjects, the animals will be removed. In addition, any adverse events will be reported immediately to the Tufts University Institutional Review Board and/or Institutional Animal Care and Use Committee as dictated by their reporting guidelines, and to the NIH. Adverse event reporting will remain the responsibility of the primary investigator, though any

staff or participants will be asked to contact the primary investigator with any questions, concerns, or suspected adverse events.

**Data Protection:** All data will be stored securely using the Tufts University CTSI REDCap system, which is HIPAA-compliant with high security (protected behind the Tufts Medical Center firewall, servers housed in a secure local data center, all web-based information encrypted). The PI will randomly assign a four digit ID number to each participant, and the key ID variable will be protected in REDCap. Questionnaire/survey data will be administered through Qualtrics (Tufts University account), a secure, encrypted survey platform ensuring protection of data. Survey data will be password-protected through the both of these platforms, and identifiable data will be restricted. The survey data files will be downloaded onto a Tufts University secure server as a data file. Physiology data from the wearable sensor will be downloaded as a data file. The file will be password protected and will only contain the participant's ID number (no identifying information).

All sessions will be video recorded to code for social referencing behaviors between participants and the therapy animals. Video files will be downloaded immediately from the camera's USB drive (and subsequently deleted from the camera) and stored in a password-protected file on a secure Tufts University server. Two copies of each video file will be stored on the Tufts server as backup in case of file corruption, and will be retained for five years. The video data will be coded with each participant's unique four-digit ID code. Behavior coding will be quantified and stored in a password-protected Excel file that contains only the participants' ID numbers. The PI, co-investigators, and research assistants participating in behavior coding will be the only individuals with access to the video data.

**Trial Monitoring:** Participant safety and data monitoring procedures will be approved by the Tufts University Institutional Review Board. The PI will directly monitor that all Tufts University IRB approved protocols for maintaining confidentiality are followed and that participant safety is maintained. All research personnel will be CITI-certified.

## Statistical Analysis Plan

### *Sample Size Calculation:*

To estimate the sample size, we used heart rate (HR) as the primary outcome and the STAI (state subscale) as the secondary outcome. There are no prior data with which to estimate the relative effect of the two intervention and control conditions on the proposed outcomes. Therefore, estimates were compiled from other research using HR as an indicator of stress response (e.g., Greenland et al., 1999). In this situation, the most conservative approach for sample size calculation is to assume a series of two-way tests. We used a mean of 75 beats per minute (bpm) with a  $SD$  of 12 bpm for baseline in all groups, assuming normal distribution, an equal number of subjects in each group, and a 0.05 significance level (alpha). With these assumptions, we will have 90% power to detect a difference of 12 bpm between any two treatment groups with 23 subjects per group, which we round to 25 per group for a total of 75 subjects in the three treatment groups. To determine the power for the STAI state subscale, based on the STAI normative data (Spielberger et al., 1983), we use a mean of 35.5 with a  $SD$  of 10.5. Using the same approach as above for HR, we will have 90% power to detect a difference of 10 between any two groups with a sample size of 25. All sample size and power calculations were performed using PASS 13 (Hintze, 2014).

### *Analyses:*

To test our confirmatory hypotheses, we conducted two three-way analyses of variance (ANOVA) with either self-reported anxiety (STAI), autonomic reactivity (electrodermal activity [EDA] and heart rate [HR]) as the dependent variable. For these outcomes, there were two between-subjects factors, condition (social, social + physical, control) and social anxiety (SA; centered continuous predictor), and one within-subjects factor, time point (1, 2, 3, 4, 5, 6). We included baseline STAI, EDA, or HR at time point 1 as a centered continuous covariate. For cognitive performance, we conducted ANOVAs that treated condition as a between-subjects categorical factor and social anxiety as a centered continuous predictor.

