*Experimental Procedure:* During the experimental session, participants will first be informed about the study, and if consent is given by the individual (and legal parent or guardian) they will be enrolled as a participant. To test the mechanism by which interacting with dogs can reduce anxiety, participants will be randomly assigned to one of three conditions that vary the nature of the interaction: 1) interaction with a stuffed toy dog (control condition); 2) social interaction (no physical contact) with a real dog; and 3) social + physical interaction with a real dog. We will not include a physical interaction only condition because it would be impractical to block the possibility for social interaction while allowing physical interaction. A stuffed toy dog will be used as an active control condition to control for the novelty of an animal-related stimulus.

Participants in all three conditions will listen to a therapy animal handler speak for several minutes about his or her dog and view a photo of the dog, in order to further control for the novelty effects of an animal stimulus and to provide a baseline rest period (20 minutes). During this rest period, participants will also complete the first self-report anxiety questionnaire and be fitted to the wearable heart rate device.

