In the control condition (1), participants will listen to the verbal presentation but there will be no animal present. Instead, there will be a stuffed toy dog (Beetz et al., 2012) and a person (to mirror the therapy dog handler). In both animal interaction conditions, one therapy dog and his or her handler will accompany the participant during all phases of the TSST-C. In the social interaction condition (2), participants will be told that the dog will be present, and they can socially interact with it at any point during the experiment (i.e., talking, social referencing), but they will not be permitted to touch the dog. In the social + physical interaction condition (3), participants will be told that the dog will be next to them and that they will be encouraged to interact socially and touch the dog during the experiment. Animal handlers are will be trained to provide consistently minimal verbal contact, to reduce the confounding effects of handler variability and distraction from the TSST-C tasks. All dog/handler teams will be approved through the Pet Partners animal therapy organization, and per the Pet Partners guidelines, all dogs will be on a 6' leash. To simulate a typical AAI environment, the handler will remain in proximity to the dog to monitor his/her behavior, but will not block the participant or interfere with the TSST-C tasks in any way.

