The primary task all participants will complete is the Trier Social Stress Task for Children (TSST-C), which involves six distinct phases: baseline, anticipation, preparation, speech, mental math, and recovery (Buske-Kirschbaum et al., 1997). The TSST-C (as well as the adult version of the TSST) has been used extensively as a robust and reliable method for inducing social stress, and variants have been used in conjunction with animal interaction (e.g., Allen et al., 2002; Polheber & Matchock, 2013). The TSST-C was originally validated for use in 10-14 year olds (Buske-Kirschbaum et al., 1997), but the protocol used in this study is a specific adaptation validated for use in adolescents up to 17 years old (Stroud et al., 2009). The TSST-C involves a public speaking task and a mental arithmetic performance challenge. During the baseline rest period (20 minutes) rest period, participants will watch a science documentary (with no animal content) on a digital tablet. Participants will then be told about the task (anticipation). Then participants will have a 5-minute preparation period, and then they will be asked to speak on an academic topic for 5 minutes (e.g., give a plot summary and interpretation of a book of their choice). They will then be asked to complete a serial subtraction mental arithmetic task for 5 minutes. Per the Stroud et al. (2009) protocol, the serial subtraction task will be adjusted for age (13-14 year olds will subtract by 11s, 15-17 year olds will subtract by 17s). If an error is made, participants will be instructed to restart from the beginning.

Finally, there will be a 30-minute recovery period where they will continue to watch the science documentary. Throughout the TSST-C, participants will be asked to self-report their anxiety levels at each of the 6 phases and will wear a watch-like wristband (Empatica E4) to continuously measure heart rate data.

Compensation for the screening process will be a \$10 gift card (duration approximately 10 minutes). Youth who meet the eligibility criteria and who participate in the experiment will be compensated with a \$75 gift card (duration of the study approximately 2 hours, not including travel time to Tufts University).

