## Measures

To test the mechanism of action for canine interaction in reducing social anxiety in adolescents, we will collect three levels of outcome data: a) self-reported experience (anxiety), b) autonomic physiological reactivity (heart rate), and c) cognitive performance (error rates on mental math task).

*Social anxiety.* The SAS-A will be used to assess overall level of social anxiety. The SAS-A was designed for use in adolescence and has been validated extensively across many samples and in multiple languages (e.g., Garcia-Lopez et al., 2011; La Greca & Lopez, 1998). The SAS-A contains 18 items that include three domains of social anxiety: fear of negative evaluation from peers, social avoidance and distress in new situations, and generalized social avoidance.

*Self-Report Experience:* Self-reported affective experience will be measured using the state scale of the State-Trait Anxiety Inventory (STAI; Spielberger et al., 1983), which is validated for use in adolescence and is commonly used with the TSST. The STAI state scale contains 20-items rated on a four-point scale, and has consistently demonstrated excellent reliability (ranging from  $\alpha = .86$  to  $.95$ ; Spielberger et al., 1983) and construct validity (Spielberger, 1989). Anxiety will be measured at six time points, during: (1) baseline, (2) anticipation (3) preparation, (4) speech, (5) mental math, and (6) recovery.

*Autonomic physiological reactivity:* Heart rate and electrodermal activity will be collected continuously using a clinical grade wristband sensor (Empatica E4; Garbarino et al., 2015).

*Cognitive Performance:* Cognitive performance during the social stressor task will be measured to understand how anxiety and AAI influence cognitive function. As recommended by existing research with the TSST paradigm (e.g., Simeon et al., 2007), we will measure cognitive performance during the mental arithmetic task by tracking the number of errors and lowest number reached by participants on the mental math task. Better performance will be characterized by fewer errors and reaching a lower number during serial subtraction.

*Demographic Characteristics:* In addition to the measures assessing the primary aims, we will also collect demographic covariate information from participants on age, sex, race/ethnicity, and current pet ownership.

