## **PROTECTION OF HUMAN SUBJECTS**

### **1. Risks to Human Subjects**

#### **a) Human subjects involvement and characteristics**

As described in the research plan, we will recruit 75 youth ages 13-17 to participate in this study. Children will be involved in this study, given that the specific aims of the study pertain to animal-assisted interventions for adolescents with social anxiety. This age range was selected due to the importance of adolescence as a critical period for the development of social anxiety.

Participants will be recruited via stratified sampling defined by scores on the Social Anxiety for Adolescents scale (SAS-A; La Greca & Lopez, 1998). We aim to recruit 25 participants in each of three strata as defined by scores of >50 (high anxiety), 36-50 (mid anxiety), and <36 (low anxiety) as recommended by La Greca (1999). Exclusion criteria include self-reported fear of or allergy to dogs. There are no exclusion criteria based on sex or race/ethnicity.

Eligible participants will be randomized into one of three conditions: 1) control group (no contact with a therapy dog); 2) social interaction with a therapy dog (no physical contact); and 3) social + physical interaction with a therapy dog. Participants in all three conditions will complete the validated Trier Social Stress Task for Children (TSST-C), which involves a public speaking task and a mental arithmetic performance challenge. During the experiment, participants will wear a clinical grade wearable sensor (similar to a watch). They will be asked to complete a self-report questionnaire of their anxiety level at baseline (State-Trait Anxiety Inventory – State scale; STAI), during each portion of the TSST-C, and at the end of the experiment. All sessions will be video recorded.

Each potential participant will be given a \$10 gift card to complete the screening process (approximately 15 minutes, can be completed at home via digital screening tool). Youth who meet the eligibility criteria will be invited to participate in the full experiment (approximately 2 hours), and will be compensated with a \$75 gift card as an incentive for participating in the study and for travel expenses (\$50 for participation, \$25 for travel costs). This compensation rate is necessary given the specific nature of our target sample and the time investment on the part of the participants, including travel to Tufts University.

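### The SAP uses the time-1 reading as both an outcome level and the covariate, so the averaged condition effect is 5/6 of its size over times 2–6; whether time 1 precedes the dog or toy is not stated

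*SAP*

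**What the plan says.** The Analyses section of the SAP describes a model for STAI, heart rate (HR) and electrodermal activity (EDA). It has condition and centered social anxiety as between-subjects factors and "one within-subjects factor, time point (1, 2, 3, 4, 5, 6"). It continues: "We included baseline STAI, EDA, or HR at time point 1 as a centered continuous covariate". Nothing there removes time 1 from the outcome, and nothing says whether a covariate × time term is fitted.

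The protocol's Measures section defines the levels: "Anxiety will be measured at six time points, during: (1) baseline, (2) anticipation (3) preparation, (4) speech, (5) mental math, and (6) recovery". Time 1 is therefore the baseline reading.

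On exposure at time 1, the protocol points two ways:

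- Participants and Procedure says of both animal conditions that "one therapy dog and his or her handler will accompany the participant during all phases of the TSST-C". It also says that the task has "six distinct phases: baseline, anticipation, preparation, speech, mental math, and recovery".
- The same section has participants in all conditions hear a handler talk during the baseline rest and "view a photo of the dog, in order to further control for the novelty effects of an animal stimulus". It adds: "During this rest period, participants will also complete the first self-report anxiety questionnaire and be fitted to the wearable heart rate device".
- The human-subjects section names baseline first, as a separate item, and then lists questionnaires "during each portion of the TSST-C, and at the end of the experiment".

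**The concern.** A reading that is both outcome and adjuster cannot add to the adjusted between-arm comparison, yet it still counts as one-sixth of the average. The sample-size text says there were no prior data on the relative effects of these conditions, so later studies are likely to take their effect sizes from this trial. It should be clear which average they are taking.

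The condition × time test is affected in another way. In a study of mechanism, a reader will take that interaction to say whether the dog acts differently in anticipation, preparation, speech, arithmetic and recovery. With baseline as a level, it also asks whether the arms diverge after baseline.

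Separately, a covariate is safe to adjust for only if assignment cannot have affected it. If the dog or toy is already with the participant at time 1, adjustment removes part of the effect being estimated.

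**Working it through.** **The plan's own figures.** Two-sample t-test, two-sided 0.05 (sidedness assumed), 90% power. HR with difference 12 and SD 12 needs 22.02, so 23 per group; power is 91.2% at 23 and 93.4% at 25. STAI with difference 10 and SD 10.5 needs 24.17, so 25 per group; power is 91.0%. Both reproduce. This calculation does not use the repeated-measures model, so the point here does not alter the stated n.

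**The 5/6 factor.** For each participant,

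mean of six = (1/6) × time 1 + (5/6) × mean of times 2–6.

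With time 1 in the model as covariate, the first term is absorbed entirely. The condition coefficient and its SE are therefore both 5/6 of those from times 2–6 with the same covariate. The same holds for condition × social anxiety. It requires complete data and equal weights, but no assumed correlation and no covariate × time term.

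- HR: 12 × 5/6 = 10.0 bpm
- STAI: 10 × 5/6 = 8.3 points

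In simulation (three arms of 25, SD 12, correlation 0.5) the estimate is 9.97 (SE 1.70) on six levels and 11.96 (SE 2.04) on five. The t statistic averages 5.91 for both, and the two agree in every data set to rounding error.

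**Where the factor comes from.** If time 1 is unexposed, its true condition effect is zero, and the six-phase average of a 12 bpm later effect really is (0 + 5 × 12)/6 = 10. A six-level average with no covariate also gives 9.9/10.0/10.0 bpm at rho 0.5/0.7/0.8.

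**Condition × time.** Assume a constant effect over times 2–6, an unexposed time 1, two arms of 25, SD 12 and equal correlation rho. Share of runs with p < 0.05:

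| | rho 0.5 | rho 0.7 | rho 0.8 |
|---|---|---|---|
| 12 bpm, six levels, covariate × time fitted | 99% | 100% | 100% |
| 12 bpm, six levels, no covariate | 96% | 100% | 100% |
| 6 bpm, six levels, covariate × time fitted | 40% | 62% | 82% |
| 6 bpm, six levels, no covariate | 36% | 59% | 80% |
| Either effect, levels 2–6 with covariate | about 5% | about 5% | about 5% |

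With no effect at any time, the six-level test rejects in about 5% of runs.

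**If time 1 is exposed.** Let d0 be the effect already present at time 1. On times 2–6, the adjusted estimate = total effect − rho × d0. The documents give neither rho nor d0, so all values are assumed. For a total effect of 12 bpm:

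| d0 | rho 0.5 | rho 0.7 | rho 0.8 |
|---|---|---|---|
| 0 | 12 | 12 | 12 |
| 6 | 12 − 3.0 = 9.0 | 12 − 4.2 = 7.8 | 12 − 4.8 = 7.2 |
| 12 (extreme) | 6.0 | 3.6 | 2.4 |

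On six levels these are multiplied by 5/6; the d0 = 6 row becomes 7.5/6.5/6.0. Main-effect power is still about 99% at d0 = 6. It is 74/43/28% at d0 = 12.

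**The covariate × time term.** With it, the adjusted time-1 effect is exactly zero. An effect equal at all six times (d0 = 12) then shows a false interaction in 32/20/14% of runs. Without it, the common slope is (1 + 5 × rho)/6. The adjusted effect at time 1 is then 12 × (5/6) × (1 − rho) = 5.0/3.0/2.0 bpm, the same as at the later times. The false interaction disappears (4/6/6%).

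**The case against.** The strongest reply is that including baseline as a level is ordinary repeated-measures ANOVA, and that the six-phase average is a legitimate quantity, correctly estimated. That stands when time 1 is unexposed: the 5/6 then comes from counting baseline as an outcome level, not from the covariate. The SAP also does not say that an averaged difference in bpm or points will be reported.

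A reader might infer a loss of power. Keeping the SD at 12 while cutting the effect to 10 bpm would suggest a fall from 93.4% to 82.3%. That is wrong, because the SE falls by the same factor.

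A reader might also call the six-level condition × time result a false positive. With an unexposed time 1 it is a true difference between baseline and later phases, and it appears without any covariate. It even bears on the protocol's question of whether contact buffers a social stressor. What remains is that one test answers two questions and cannot say which.

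Finally, a reader might conclude that the dog was certainly in the room at baseline. The all-phases wording and the list of phases, taken literally, say so. The photo shown to everyone and the separate listing of baseline fit a later entry. The common baseline mean in the sample-size text is a planning input and is no evidence either way. Nor do the talk and the documentary necessarily conflict: the talk lasts only minutes of a 20-minute rest.

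**Conclusion.** The double use of time 1 is explicit in the SAP. Its effect on the averaged condition estimate and on condition × social anxiety is exactly 5/6 relative to times 2–6, given complete data and equal weights. It does not change the main-effect t, p or power, does not raise type I error under the null, and is not a bias if time 1 is unexposed. The practical harm is a diluted estimate and an interaction test that is hard to interpret.

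The exposure question is open, because no section gives the entry time. If time 1 precedes the dog or toy, there is no shift. If it does not, the covariate is affected by treatment and the total effect shifts by rho × d0, a size that rests wholly on assumptions. A false condition × time interaction, for an effect equal at all six times, arises only if covariate × time is fitted, which the SAP does not state. The point should be fixed, but it does not invalidate the main test.

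**What to change.** Analyse time points 2–6 as the outcome, with time 1 as covariate only, and state whether covariate × time is included. Condition × time then asks whether the effect differs between phases. Show the baseline-to-stress rise separately, for example descriptively. This needs no new data and costs no main-effect power; the downside is one fewer time level.

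Reconcile the protocol's Participants and Procedure section with its human-subjects section on when the dog or toy enters relative to the first STAI and the baseline HR and EDA. If time 1 was exposed, dropping level 1 is not enough. State whether the target is the total effect or the change from rest, and report results with and without the time-1 covariate. Dropping the covariate widens the interval. For the mean of times 2–6, the unadjusted SE is 12 × √[((1 + 4 × rho)/5) × 2/25] = 2.63/2.96/3.11 bpm at rho 0.5/0.7/0.8. With an unexposed covariate it would be 12 × √[((1 + 4 × rho)/5 − rho²) × 2/25] = 2.01/1.76/1.52.

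The SAP is written in the past tense, so sessions may be complete. Any change made after results were seen should be labelled post hoc.
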